**Table 6 - Analyses of adverse events**

Type of AE	MedDRA levels
All unsolicited AE within 28 days	Primary SOC and PT
All unsolicited AR within 28 days	Primary SOC and PT

Type of AE	MedDRA levels
Unsolicited AEs within 28 days occurring in >1% of subjects	Primary SOC and PT
Unsolicited non-serious AE within 28 days	Primary SOC and PT
Unsolicited non-serious AR within 28 days	Primary SOC and PT
All and related AE leading to study discontinuation within 28 days	Primary SOC and PT
SAE	Overview a
	Primary SOC and PT

a Will include the following AE categories: all SAEs and related SAEs within 7 days after vaccine injection, within 28 days after vaccine injection, and during the study

### **Analysis of deaths**

The summary of death will be presented above in safety overview.

### **Analysis of adverse events of special interest (AESIs)**

AESIs will be selected for analyses as indicated in [Table 7](#). Number (%) of subjects experiencing at least one event within 28 days after vaccine injection and during the study will be provided for each event of interest. Tables will be sorted by SOC and PT as indicated in [Table 5](#).

**Table 7 - Selections for AESIs**

AESIs	Selection (PT)
Guillain-Barré syndrome (GBS)	Chronic inflammatory demyelinating polyradiculoneuropathy Demyelinating polyneuropathy Guillain-Barre syndrome Miller Fisher syndrome
Encephalitis/myelitis (including transverse myelitis)	Myelitis Myelitis transverse Encephalitis is using the narrow Standardised MedDRA Query (SMQ) term "Noninfectious encephalitis" (MedDRA Version 23.1)
Bell's palsy	Facial palsy Facial paralysis Facial paresis Bell's palsy
Optic neuritis	Optic neuritis Optic neuropathy
Brachial neuritis	Brachial neuritis Brachial plexopathy Neuralgic amyotrophy Parsonage Turner Syndrome

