5 INVESTIGATIONAL PLAN

5.1 DESCRIPTION OF THE OVERALL STUDY DESIGN AND PLAN

5.1.1 Study Design

QHD00010-EFC15150 will be a Phase III, randomized, modified double-blind, active controlled, multi-center study to be conducted in approximately 2100 healthy adults 60 years of age and older to assess the immunogenicity and safety of QIV-HD administered by IM route in comparison to the local QIV-SD administered by SC route as a control arm.

Interactive response technology (IRT) will be used to randomly assign subjects to either of the 2 study groups and to assign subject numbers in each of the groups.

A total of approximately 2100 subjects are planned to be enrolled and randomized in a 1:1 ratio as follows:

- Group 1 (QIV-HD by IM route): n = 1050
- Group 2 (QIV-SD by SC route): n = 1050

An unblinded administrator at each site will administer the vaccine.

All subjects will provide a pre-vaccination (baseline) blood sample at Visit (V) 01 (Day [D] 0) and a post-vaccination blood sample at V02 (D28 [+ 7 days]) for HAI testing.

Solicited reactions will be collected up to 7 days after vaccination and unsolicited AEs will be collected up to V02. Serious adverse events (SAEs) and adverse events of special interest (AESIs) will be collected throughout the study (D0 through V02).

Electronic data capture (EDC) will be used for the collection of data.

Note: AESIs will be captured as SAEs. These include new onset of Guillain-Barré syndrome, encephalitis / myelitis (including transverse myelitis), Bell's palsy, optic neuritis, and brachial neuritis.

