9.2.2.2 Safety Endpoints

The secondary endpoint(s) for the evaluation of safety are:

- Occurrence, nature (Medical Dictionary for Regulatory Activities [MedDRA] preferred term [PT]), duration, intensity, and relationship to vaccination of any unsolicited systemic AEs reported in the 30 minutes after vaccination.
- Occurrence, time to onset, number of days of occurrence, maximum intensity, action taken, and whether the reaction led to early termination from the study, of solicited (prelisted in the subject's diary card and CRB) injection site reactions and systemic reactions occurring up to 7 days after vaccination.
- Occurrence, nature (MedDRA PT), time to onset, duration, intensity, relationship to vaccination (for systemic AEs only), and whether the event led to early termination from the study, of unsolicited AEs up to 28 days after vaccination.
- Occurrence, nature (MedDRA PT), time to onset, seriousness criteria, relationship to vaccination, outcome, and whether the event led to early termination from the study, of SAEs throughout the study.
- Occurrence, nature (MedDRA PT), and relationship to vaccination of AESIs throughout the study.

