9.2.2.3.4 Adverse Events of Special Interest

AESIs will be captured as SAEs (collected throughout the study). These include new onset of [\(31\)](#):

- Guillain-Barré syndrome
- encephalitis/myelitis (including transverse myelitis)
- Bell’s palsy
- optic neuritis
- brachial neuritis

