10.2 GUIDELINES FOR REPORTING ADVERSE EVENTS OF SPECIAL INTEREST

For AESI, the Sponsor is to be informed immediately (i.e., within 24 hours), as per SAE notification guidelines described in [Section 10.1](#), even if a seriousness criterion is not met, using the corresponding pages of the CRF (to be sent) or screens in the CRB.

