#### **4.7.2 Adverse events**

##### **General common rules for adverse events**

All adverse events (AEs) will be coded to a lower-level term (LLT), preferred term (PT), and associated primary system organ class (SOC) using the MedDRA version currently in effect at Sanofi at the time of database lock.

The AE tables will be sorted as indicated in [Table 5](#).

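### SAP Table 7 selects AESIs by a term list that does not match the protocol's definition, so an infectious-coded encephalitis reported by a site would be missing from the AESI results

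*SAP*

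**What the plan says.** Protocol 9.2.2.3.4 reads "AESIs will be captured as SAEs (collected throughout the study). These include new onset of" and then lists Guillain-Barré syndrome, encephalitis/myelitis (including transverse myelitis), Bell's palsy, optic neuritis and brachial neuritis. The synopsis, the Table of Study Procedures and section 5.1.1 give the same five. None of them limits encephalitis by cause.

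Protocol 10.2 requires the site to notify the sponsor of an AESI within 24 hours, "even if a seriousness criterion is not met". Protocol 9.2.2.2 makes this a secondary safety endpoint: "Occurrence, nature (MedDRA PT), and relationship to vaccination of AESIs throughout the study". SAP Table 2 repeats it.

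SAP 4.7.2 then states that "AESIs will be selected for analyses as indicated in" Table 7, a list of preferred terms under the same five headings. For encephalitis the entry is "Encephalitis is using the narrow Standardised MedDRA Query (SMQ) term" Noninfectious encephalitis, MedDRA version 23.1. All adverse events are coded "using the MedDRA version currently in effect at Sanofi at the time of database lock".

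The SAP's version history declares no major change to the statistical features, and Appendix 2 (section 5.2) records none.

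**The concern.** The protocol identifies AESIs by the site's recognition of a new-onset condition. The SAP identifies them by preferred term, drops the new-onset condition, and uses terms that are narrower than the protocol in one place and wider in others. The SAP does not say that a site-reported AESI outside Table 7 stays in the AESI results. Nor does it say whether Table 7 is applied to every coded adverse event or only to events that sites reported as AESIs.

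At stake is whether the AESI table and the AESI rows of the safety summaries report the events that the protocol defined and collected. For events this closely watched, readers look first at whether the count is zero.

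**Working it through.** No sample size, power or error-rate figure bears on this point, so there is none to reproduce. The check is a comparison of the two texts, followed by one calculation for scale.

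**Step 1. The two definitions side by side.**

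| Protocol condition (new onset) | Terms selected in SAP Table 7 | Relation |
|---|---|---|
| Guillain-Barré syndrome | Guillain-Barré syndrome, Miller Fisher syndrome, chronic inflammatory demyelinating polyradiculoneuropathy, demyelinating polyneuropathy | Wider: the last two are not named in the protocol |
| Encephalitis/myelitis | Myelitis, transverse myelitis, narrow Noninfectious encephalitis query | Myelitis agrees; encephalitis is narrower |
| Bell's palsy | Bell's palsy, facial palsy, facial paralysis, facial paresis | Wider on paper, but protocol 1.3.2 treats facial palsy and Bell's palsy as one item |
| Optic neuritis | Optic neuritis, optic neuropathy | Wider on paper, but protocol 1.3.2 pairs the two |
| Brachial neuritis | Brachial neuritis, neuralgic amyotrophy, Parsonage Turner syndrome, brachial plexopathy | Brachial plexopathy is not named in the protocol |

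**Step 2. An event that drops out.** Take a new-onset encephalitis that a site reports as an AESI and that codes to an infectious term.
- It meets the protocol's wording.
- By the name of the query, it is outside Table 7.
- If Table 7 is run on all coded events, it is not selected. If Table 7 is run only on site-reported AESIs, it is filtered out. The result is the same on either reading.
- Because the site captured it as an SAE, it still appears in the SAE summaries by system organ class and preferred term (SAP Table 6) and by seriousness criterion and outcome. It is lost only from the AESI table and the AESI overview rows.

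**Step 3. An event that enters.** Take an event that codes to a Table 7 term but that the site did not report as an AESI, because the protocol does not name the condition or because it is not new onset.
- If Table 7 is run on all coded events, it is counted.
- If Table 7 is run only on site-reported AESIs, it is not.
- A route exists for events that are not new onset: under protocol 9.2.2.1, a pre-existing condition that worsens or recurs more often is a reportable adverse event.
- Programming could not screen these out reliably, because protocol 5.2.6 leaves medical history uncoded and without dates. Someone must look at the case.

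**Step 4. Scale.** Inputs: 1050 subjects per group (protocol 5.1.1), before any exclusion from the safety analysis set, and the exact Clopper-Pearson limits of SAP 5.4.7. With r events in n subjects, the lower limit is 1 − Beta(0.975; n − r + 1, r), taken as 0 when r = 0, and the upper limit is Beta(0.975; r + 1, n − r).

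| Events in one arm | Rate | 95% CI |
|---|---|---|
| 0 | 0.00% | 0.00 to 0.35% |
| 1 | 1/1050 = 0.10% | 0.00 to 0.53% |
| 2 | 2/1050 = 0.19% | 0.02 to 0.69% |

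One event dropped or added moves the rate by about 0.1 percentage point, and the intervals overlap almost entirely. What changes is whether the row reads none or some.

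**The case against.** The best defence is that a prespecified term list is a sound way to find AESIs. The endpoint itself is expressed in preferred terms, the data items listed in protocol 9.2.2.3.3 include seriousness but no AESI flag, and a list protects against sites that fail to report. All of that stands, and it is a reason to keep Table 7. It does not explain why an event that a site did report should be left out.

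A second defence is that an AESI is by definition a concern specific to the product, so limiting encephalitis to noninfectious causes merely carries out the intent. That may be so, but the protocol never states the limit and the SAP does not declare it. The source cited for the list is outside the documents.

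Several stronger readings are tempting but not supported:
- *An encephalitis would vanish from the safety report.* It would not; the SAE tables would still show it.
- *An event coded simply as encephalitis would be missed.* The query's contents are not in the documents, so this cannot be said.
- *AESIs will appear that are absent from the SAE tables.* This requires Table 7 to be run on all coded events, which is the plain reading but is not stated.
- *Facial paresis and optic neuropathy are wrongly included.* The pairings in protocol 1.3.2 make them reasonable case-finding terms.
- *The fixed MedDRA version will cause missed matches.* The version in effect at lock is not given and may be 23.1, so no mismatch is shown.

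**Conclusion.** The point holds, and it is limited. Table 7 is narrower than the protocol for encephalitis, and the resulting loss from the AESI results occurs however the table is applied. That conclusion assumes only that a query named Noninfectious encephalitis excludes infectious terms. Wrong entry is conditional: it needs Table 7 to be run on all coded events, and its clearest examples are chronic inflammatory demyelinating polyradiculoneuropathy, demyelinating polyneuropathy, brachial plexopathy and any event that is not new onset.

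The endpoint is secondary and descriptive with no hypothesis tested, so the primary analysis and its error rate are untouched. A reader might infer that one misplaced event would overturn the safety result. The calculation does not support that, and the documents give no expected number of AESIs. The change should be made because the endpoint as analysed need not be the endpoint as defined, and no departure is recorded.

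**What to change.** In SAP 4.7.2:
1. Define the AESI table and overview rows as all events that sites reported as AESIs under protocol 9.2.2.3.4 and 10.2, whatever their preferred term.
2. Keep the Table 7 search, state that it is run on all coded adverse events, and present matches that sites did not report as AESIs in a separate, labelled table or listing. Check each for new onset in the blind data review already anticipated in protocol 11.3.
3. Run the encephalitis query in the MedDRA version used for coding.
4. Record the difference from the protocol in SAP 5.2.

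The cost is SAP wording, one small table or listing and a few blinded case checks. No new subject data are needed, since the reports are already required under protocol 10.2. Because the documents do not show an AESI flag on the adverse event form, data management should confirm before lock how those reports are identified in the database.

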#### **4.7.3 Additional safety assessments**

##### **4.7.3.1 *Laboratory variables, vital signs and electrocardiograms (ECGs)***

Not applicable

### **4.8 OTHER ANALYSES**

#### **4.8.1 Assessment of impact of COVID-19 pandemic**

In order to assess an impact of Coronavirus Disease 2019 (COVID-19) pandemic on study conduct, the number (%) of subjects in the following categories will be also summarized on enrolled subjects.

- Subjects with a CRF
- Subjects impacted by COVID-19 pandemic situation
- Subjects with at least one major/critical protocol deviation due to COVID-19 pandemic situation, and each detailed deviation
- Subjects who discontinued the trial with following reasons of early termination due to COVID-19
  - Adverse event
  - Protocol deviation
  - Lost to follow-up
  - Withdrawal by subject
- Visit disposition at each visit (Visit 1 and Visit 2)
  - COVID-19 Visit not done
  - COVID-19 Visit partially done: blood sample not performed, vaccination not performed, and no solicited safety data available
  - COVID-19 At least one procedure out of time window: blood sample out of time window, vaccination out of time window, and visit date out of time window
  - COVID-19 No procedure done on site
  - COVID-19 At least one procedure done by phone
  - COVID-19 At least one procedure done at home

### **4.9 INTERIM ANALYSES**

No interim / preliminary analyses are planned. There will be one statistical analysis conducted after the end of the study (D28).

## 5 SUPPORTING DOCUMENTATION

### 5.1 APPENDIX 1 LIST OF ABBREVIATIONS

Ab:	antibody
AE:	adverse event
AESI:	adverse event of special interest
ANCOVA:	analysis of covariance
AR:	adverse reaction
CI:	confidence interval
COVID-19:	Coronavirus Disease 2019
CRB:	case report book (all the case report forms for a subject)
CRF:	case report form
CSR:	clinical study report
D:	Day
FAS:	Full Analysis Set
GBS:	Guillain-Barré syndrome
GM:	geometric mean
GMT:	geometric mean titer
GMTR:	geometric mean of individual titer ratio
HA:	hemagglutinin
HAI:	hemagglutination inhibition
IM:	intramuscular
IRT:	interactive response technology
LLOQ:	lower limit of quantification
LLT:	lower-level term
MCAR:	missing completely at random
MD:	missing data
MedDRA:	Medical Dictionary for Regulatory Activities
MHLW:	Ministry of Health, Labour and Welfare
NH:	Northern Hemisphere
NM:	non-measurable
NSAIDs:	non-steroidal anti-inflammatory drugs
PPAS:	Per-Protocol Analysis Set
PT:	preferred term
Q1:	first quartile
Q3:	third quartile
QIV-HD:	high-dose quadrivalent influenza vaccine
QIV-SD:	standard-dose quadrivalent influenza vaccine
RCDC:	reverse cumulative distribution curve
SAE:	serious adverse event
SafAS:	Safety Analysis Set
SAP:	statistical analysis plan

SC:	subcutaneous
SD:	standard deviation
SMQ:	Standardised MeDRA Query
SOC:	system organ class
ULOQ:	upper limit of quantification
US:	United States
V:	visit
VRBPAC:	Vaccines and Related Biological Products Advisory Committee
WHO:	World Health Organization
WHO-DD:	World Health Organization-drug dictionary

## 5.2 APPENDIX 2 CHANGES TO PROTOCOL-PLANNED ANALYSES

This section summarizes major statistical changes in the protocol amendment(s).

**Table 8 - Major statistical changes in protocol amendment(s)**

Amendment Number	Approval Date	Changes	Rationale
1	24-Apr-2020	No changes in protocol amendment	

## 5.3 APPENDIX 3 DEMOGRAPHICS AND BASELINE CHARACTERISTICS, PRIOR OR CONCOMITANT MEDICATIONS

### *Demographics, baseline characteristics, medical surgical history*

The following demographics and baseline characteristics, and medical history will be summarized using descriptive statistics in the randomized population. The demographics and baseline characteristics will also be summarized in the FAS, PPAS, and SafAS.

#### Demographic and baseline characteristics

- age in years as quantitative variable and in categories (60 to <65, ≥65, 65 to <75, ≥75)
- gender (Male, Female) and the ratio
- race (White, Black, Asian, American Indian or Alaska Native, Native Hawaiian or other Pacific Islander, Multiple, Not reported, and Unknown)
- weight in kilograms
- BMI (body mass index) as quantitative variable and in categories (<18.5, 18.5 to 24.9, ≥25.0)

Medical history includes conditions/illness for which the subject is or has been followed by a physician or conditions/illnesses that could resume during the course of the study or lead to an

SAE or to a repetitive outpatient care will be collected in the case report book (CRB). The medical history will not be coded using the MedDRA.

Influenza disease history during 2019 through 2020 season, and history of influenza vaccination during 2019 through 2020 season, pneumococcal vaccination and shingles vaccination will also be collected.

### ***Concomitant medications***

All reportable medications will be coded using the World Health Organization-Drug Dictionary (WHO-DD) using the version currently in effect at Sanofi at the time of database lock.

Documentation in the CRB of ongoing concomitant medication(s) will be limited to specific categories of medication(s) of interest beginning on the day of vaccination this may include medications of interest that were started prior to the day of vaccination.

Reportable medications will be collected in the CRB from the day of vaccination to the end of the study (D28 [+7 days]).

Reportable medications include medications that impact or may impact the consistency of the safety information collected after any vaccination and/or the Ab response to vaccination. Four standard categories of reportable medications are defined:

- Category 1: medications impacting or that may have an impact on the evaluation of the safety (e.g., antipyretics, analgesics, and non-steroidal anti-inflammatory drugs [NSAIDs])
- Category 2: medications impacting or that may have an impact on the immune response (e.g., other vaccines, blood products and immune globulins, immune-suppressors, immune-modulators with immunosuppressive properties, antiproliferative drugs such as DNA synthesis inhibitors)
- Category 3: medications impacting or that may have an impact on both the safety and the immune response (e.g., steroids/corticosteroids)
- Category 4: the statin family of anti-hyperlipidemia medications (e.g., atorvastatin, rosuvastatin, simvastatin, pravastatin, and fluvastatin)

Following treatments are the protocol-restricted during the study period:

- Immunosuppressive therapy, such as anti-cancer chemotherapy or radiation therapy, or long-term systemic corticosteroid therapy (prednisone or equivalent for more than 2 consecutive weeks)
- Immune globulins, blood or blood-derived products
- Any other vaccines

The reportable medications will be summarized for the randomized subjects. The summary will be presented based on the use of any medication and each category, and the medication considered by the sponsor as prophylactic, protocol-restricted treatment, and ongoing at study termination.

## **Protocol-prohibited therapy, medication or vaccines**

In general, the “prohibited” variable is not derived. All concomitant medications are reviewed by the clinical team and the value of “prohibited” variable is determined before database lock by the clinical team according to the treatments defined above as “protocol-restricted.”

If the above protocol-restricted therapy, medication or vaccines are received during study participation, it may impact the corresponding immunogenicity analyses.

## **5.4 APPENDIX 4 DATA HANDLING CONVENTIONS**

### **5.4.1 General conventions**

#### *Duration of the study*

The duration of the study is computed in days as follows:

Maximum (Visit dates, Termination date) – minimum (Date of Visit 1) + 1.

#### *Subject duration*

The duration of a subject participation in the study is computed as follows:

Maximum (Date of visits, termination date) – Date of Visit 1 + 1.

#### *Time interval*

The time interval between two visits/vaccinations/blood samples is computed as follow:

Last date – earlier date.

### **5.4.2 Data handling conventions for safety variables**

#### **5.4.2.1 *Solicited Reactions***

##### *Daily intensity*

All daily records for solicited reactions will be derived into daily intensity according to the following classification: None, Grade 1, Grade 2, Grade 3, or Missing. The category of Unknown will be considered Missing if Unknown is recorded.

For measurable injection site reaction (Erythema/Swelling/Induration/Bruising):

- Grade 1:  $\geq 25$  to  $\leq 50$  mm
- Grade 2:  $\geq 51$  to  $\leq 100$  mm
- Grade 3:  $> 100$  mm

For measurable systemic reactions (Fever):

- Grade 1:  $\geq 38.0$  to  $\leq 38.4$  °C, or  $\geq 100.4$  to  $\leq 101.1$  °C
- Grade 2:  $\geq 38.5$  to  $\leq 38.9$  °C, or  $\geq 101.2$  to  $\leq 102.0$  °C
- Grade 3:  $\geq 39.0$  °C, or  $\geq 102.1$  °C

For the derivation of daily intensities the following sequential steps will be applied:

For solicited reactions (except Fever/Pyrexia) with an investigator presence recorded as “No” and with all daily records missing, all daily intensities will be derived as “None”.

For non-measurable solicited reactions, daily intensities will correspond to daily records reported in the clinical database. For measurable solicited reactions the daily measurements reported in the clinical database will be converted based upon the intensity scales defined in the protocol; this assumes a reaction that is too large to measure (non-measurable, “NM”) is Grade 3. Note that the intensity could be considered as “None” (not a reaction) in the analysis despite being considered a reaction by the investigator (e.g., swelling measurement  $>0$  mm but  $<25$  mm in adults).

Note: The maximum intensity during the ongoing period is derived from the record of the maximum intensity/measurement after the end of the solicited period following the rule described above.

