⁸ The term “life-threatening” refers to an event in which the subject was at risk of death at the time of the event; it does not refer to an event which hypothetically might have caused death if it were more severe.

⁹ All medical events leading to hospitalizations will be recorded and reported as SAEs, with the exception of hospitalization planned before inclusion into the study or outpatient treatment with no hospitalization.

¹⁰ “Persistent or significant disability or incapacity” means that there is a substantial disruption of a person’s ability to carry out normal life functions.

- Is an important medical event (IME)

Medical and scientific judgment should be exercised in deciding whether expedited reporting is appropriate in other situations, such as IMEs that may not be immediately life-threatening or result in death or hospitalization but may jeopardize the health of the subject or may require intervention to prevent one of the other outcomes listed in the definition above. These IMEs should also usually be considered serious. Examples of such events include allergic bronchospasm requiring intensive treatment in an emergency room or at home, blood dyscrasias or convulsions that do not result in inpatient hospitalization, or the development of drug dependency or drug abuse, new-onset diabetes, or autoimmune disease.

Adverse Reaction (AR):

All noxious and unintended responses to a medicinal product related to any dose should be considered adverse reactions (ARs).

(The phrase “responses to a medicinal product” means that a causal relationship between a medicinal product and an AE is at least a reasonable possibility.)

The following additional definitions are used by the Sponsor:

Immediate Event/Reaction:

Immediate events are recorded to capture medically relevant unsolicited systemic AEs (including those related to the product administered) that occur within the first 30 minutes after vaccination.

Solicited Reaction:

A solicited reaction is an “expected” AR (sign or symptom) observed and reported under the conditions (nature and onset) prelisted in the protocol and CRB.

By definition, solicited reactions are to be considered as being related to the product administered.

For injectable vaccines, solicited reactions can either be solicited injection site reactions or solicited systemic reactions.

The assessment of these reactions by the investigator is mandatory.

Unsolicited AE / AR:

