### ***Presence***

Presence is derived from the maximum intensity of the period considered:

- No presence : None
- Presence : Grade 1, Grade 2 or Grade 3
- Unknown or Missing presence : Missing

Subjects with at least one non-missing presence for a specific endpoint will be included in the analysis. Conversely, those without a non-missing presence will not be included in the analysis of the endpoint.

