## **5.4.4 Missing data**

For categorical variables, patients with missing data are not included in calculations of percentages unless otherwise specified. When relevant, the number of patients with missing data is presented.

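### The SAP uses the investigator's answer on a solicited reaction without diary data only when it is negative, which lowers reported rates for the five reactions graded by effect on activities

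*SAP*

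**What the plan says.** Five parts of the SAP together decide what happens to a subject who has an investigator answer but no daily values.

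- **Daily intensity (5.4.2.1), first step.** Its scope is "For solicited reactions (except Fever/Pyrexia"). For those reactions, "with an investigator presence recorded as “No” and with all daily records missing, all daily intensities will be derived as “None".
- **Daily intensity, next step.** For non-measurable reactions, "daily intensities will correspond to daily records reported in the clinical database". Measurable reactions are converted from the recorded measurement, and a size above 0 but below 25 mm becomes *None*.
- **Presence (5.4.2.1).** "Presence is derived from the maximum intensity of the period considered", not from the investigator's answer. *Missing* intensity gives *Missing* presence, and "those without a non-missing presence will not be included in the analysis of the endpoint".
- **5.4.4 Missing data.** For categorical variables, "patients with missing data are not included in calculations of percentages unless otherwise specified".
- **5.4.4.1 Intensity.** For solicited reactions this only points back to Daily intensity.

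On the protocol side, section 9.2.2.1 says of solicited reactions: "The assessment of these reactions by the investigator is mandatory". Section 9.2.2.2 makes their occurrence a secondary safety endpoint. Section 5.1.4 has the diary card collected at V02.

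**The concern.** The same field is trusted in one direction and ignored in the other. A known non-reactor without daily values is kept and a known reactor without daily values is dropped. Because the investigator's assessment is mandatory and the card comes back only at V02, an investigator answer without diary data can arise, for example after early termination or a lost card.

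The rule also sits badly with the rest of the SAP. Section 5.4.4.1 says missing safety data are generally not replaced, yet the *No* step is a replacement, and only towards fewer reactions. Missing causality is counted as related, which is the cautious direction. An unsolicited non-serious event with a verbatim term and no intensity is still counted as an event, with its intensity left missing (5.4.2.2 and 5.4.4.1). A solicited reaction confirmed by the investigator gets less weight than that.

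At stake is the accuracy of the reactogenicity percentages, which describe the product's tolerability.

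**Working it through.** The plan states no expected solicited-reaction rate and no expected share of missing diary data, so there is no plan figure to reproduce. Its 5% attrition (Protocol 12.5, Table 3) refers to the FAS, and its 5% ceiling on missing data (Protocol 12.3.2) refers to immunogenicity. In what follows *p* and *m* are assumptions.

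**Step 1: trace the two cases for a non-measurable reaction.**

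| Investigator answer, no daily records | Daily intensity | Presence | In the percentage? |
|---|---|---|---|
| *No* | *None* (first step) | No | Yes, as a non-event |
| *Yes* | *Missing* (no step applies) | *Missing* | No |

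**Step 2: formula.** Let *p* be the rate when the investigator's answer is accepted in both directions, and *m* the share of *Yes* subjects without any daily record. All *No* subjects are kept.

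- Events kept: p(1 − m)
- Denominator kept: p(1 − m) + (1 − p) = 1 − pm
- Reported rate: p(1 − m)/(1 − pm), which is below p whenever m > 0 and 0 < p < 1

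**Step 3: numbers.**

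| Assumed p | m = 1% | m = 2% | m = 5% | Shift at 5% |
|---|---|---|---|---|
| 10% | 9.9% | 9.8% | 9.5% | −0.45 points |
| 20% | 19.8% | 19.7% | 19.2% | −0.81 points |
| 30% | 29.8% | 29.6% | 28.9% | −1.07 points |
| 40% | 39.8% | 39.5% | 38.8% | −1.22 points |
| 50% | 49.7% | 49.5% | 48.7% | −1.28 points |

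For p = 40% and m = 5%: 0.40 × 0.95/(1 − 0.02) = 0.380/0.980 = 38.8%. In counts, with 1050 per arm and p = 30%, 315 subjects react. Dropping 16 of them gives 299/1034 = 28.9% instead of 30.0%.

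**Step 4: variations, all assumed.**

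- *Every subject without records is a reactor.* With m now the share of all subjects, the rate is (p − m)/(1 − m). At p = 40% this is 0.38/0.98 = 38.8% for m = 2% and 0.35/0.95 = 36.8% for m = 5%.
- *Unequal arms.* With p = 40% in both arms and m = 5% against 1%, the reported rates are 38.8% and 39.8%, an apparent difference of about 1.0 point.
- *Composite rows.* If the only reaction is the undocumented *Yes* and the other items are *None*, the subject may remain in the any-reaction row as a non-event. The rate is then p(1 − m): 28.5% for p = 30%, m = 5%. The SAP does not say how composites treat this mix.

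**Step 5: size-graded reactions.** Suppose 10% of subjects have a reaction of at least 25 mm and 20% have one below 25 mm.

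- If 5% of only the small ones lack records, 0.20 × 0.05 = 1% of subjects are dropped. The reported rate is 0.10/0.99 = 10.1%, above the true 10%.
- If 5% of both sizes lack records, the rate is 0.095/0.985 = 9.6%, below it.

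So the sign is not determined here. Counting every unmeasured *Yes* as present would give 0.10 + 0.01 = 11.0% in either case, which is too high.

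**The case against.** **Blank fields may be structural.** The SAP does not equate missing daily records with a lost card. If the investigator ticks *No*, there may be nothing to grade. The fever exemption fits this reading, since temperature is recorded daily whether or not there is fever. This may well explain the *No* step, and that step can stay. It supplies no rule for *Yes*.

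**Sites should close the gap first.** Protocol 13.2 requires verbal clarification of missing diary data. Sections 11.1 and 11.2 add an interview, an explanation of all missing information, and queries. Section 5.2.11 requires contact with subjects who terminate because of an AE. This stands as a reason to expect few cases. It does not change what the derivation does with those that remain.

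**Stronger readings.** A reader might infer that the rule can only lower every solicited rate. Step 5 shows that this fails for the four size-graded reactions, and fever is dropped under either answer. A reader might also infer that someone who leaves because of a reaction disappears from the safety report. SAP 5.4.2.4 counts such a subject in the safety overview from the termination form alone, without a diary grade. The SOC/PT table of events leading to discontinuation does require at least Grade 1, so the event could still be absent there. Finally, the rule is the same in both arms, and nothing in the documents shows that missing records would differ between them.

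**Low consequence.** Safety is secondary and descriptive, with no test (Protocol 12.1.2.1, SAP 4.7). This stands and limits the weight of the point.

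**Conclusion.** The point holds for pain, headache, malaise, myalgia and shivering. The downward direction follows from the text once any investigator *Yes* lacks all daily records, taking that *Yes* as correct. The exclusion results from silence in Daily intensity combined with the Presence rule, not from an express instruction to drop such subjects. It still produces a wrong percentage if the stated rules are followed.

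The size is probably small. For single reactions it is at most about 1.3 points in the Step 3 table, where m does not exceed 5%. It could be larger in composite rows or if subjects without records are mostly reactors. Neither *p* nor *m* comes from the documents. For erythema, swelling, induration and bruising, the defect is an unstated rule with an undetermined direction, not a demonstrated downward bias. The change is worth making because it is cheap and the affected percentages are a named secondary endpoint.

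**What to change.** Amend SAP 5.4.2.1, under Daily intensity and Presence, before unblinding.

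1. **Non-measurable reactions** (pain, headache, malaise, myalgia, shivering): if the investigator's answer is *Yes* and all daily records are missing, set presence to Yes. Show maximum intensity, onset and number of days as *Missing*. Count the subject in the any-reaction and composite rows.
2. **Size-graded reactions** (erythema, swelling, induration, bruising): keep intensity *Missing* in the main table. Report the number of such *Yes* cases by arm, and add a sensitivity table that counts them as present.
3. Leave the existing *No* step and the fever exemption as they are.

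The cost is a short text change, one derivation line, a *Missing* intensity category, a *Missing* row in Tables 9 and 10 (Table 11 already has one), a count by arm and one sensitivity table. No new data are collected. The downside for the sponsor is that reported reaction rates become slightly less favourable. If no such subjects exist, no rate changes.
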